13.4.4.7 Dermal Safety

The number and percentage of subjects with findings related to dermal safety including adhesion, irritation, discomfort, and adhesive residue will be summarized. A by-subject listing of individual dermal safety findings will also be provided.

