This statistical analysis plan (SAP) describes the planned analysis and reporting for Noven Pharmaceuticals, Inc. protocol number HP-5000-US-05 (*A 4-week, Randomized, Double-blind, Multicenter, Placebo-controlled Phase 2 Study to Evaluate the Efficacy and Safety of HP-5000 in Subjects with Osteoarthritis (OA) of the Knee*), dated 12-Jan-2018, Amendment 2. Reference materials for this statistical plan include the protocol and the accompanying sample data collection documents^{1,2}. Operational aspects related to collection and timing of planned clinical assessments are not repeated in this SAP unless relevant to the planned analysis.

The structure and content of this SAP provides sufficient detail to meet the requirements identified by the Food and Drug Administration (FDA), European Medicines Agency (EMA), and International Conference on Harmonization (ICH) of Technical Requirements for Registration of Pharmaceuticals for Human Use: Guidance on Statistical Principles in Clinical Trials³, International Conference on Harmonization; Statistical Principles for Clinical Trials: Addendum on Estimands and Sensitivity Analysis in Clinical Trials⁴. All work planned and reported for this SAP will follow internationally accepted guidelines, published by the American Statistical Association⁵ and the Royal Statistical Society⁶, for statistical practice.

The planned analyses identified in this SAP will be included in clinical study reports (CSRs), regulatory submissions, or future manuscripts. Also, post-hoc exploratory analyses not necessarily identified in this SAP may be performed to further examine study data. Any post-hoc or unplanned, exploratory analysis performed will be clearly identified as such in the final CSR.

The statistical plan described hereafter is an *a priori* plan. It will be submitted to file prior to any unblinded inferential or descriptive analysis of data pertaining to Noven Pharmaceuticals, Inc.'s study HP-5000-US-05.

2. Study Objectives and Endpoints

This is a phase II study with the goal to evaluate efficacy, safety (including dermal), and PK of two active treatments: HP-5000-[REDACTED] (diclofenac sodium) [REDACTED] topical patch [REDACTED] and HP-5000-[REDACTED] (diclofenac sodium) [REDACTED] topical patch [REDACTED]. [REDACTED] will be chosen to advance to phase III development.

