4.1. Introduction

Data processing, tabulation of descriptive statistics, calculation of inferential statistics, and graphical representations will be performed using SAS® (release 9.4 or higher). If the use of other software is warranted, the final statistical methodology report will detail what software was used for what purposes.

Continuous variable summaries will include the number of subjects or patches (n) with non-missing values, mean, standard deviation (SD), median, minimum, and maximum. Where appropriate, estimates will be presented with 95% confidence intervals (CIs) and standard error (SE).

Categorical variable summaries will include the frequency and percentage of subjects or patches that are in the particular category or each possible value. In general the denominator for the percentage calculation will be based upon the study population for the specified treatment group and overall, unless otherwise specified. The denominator for by-visit displays will be the number of subjects (or patches) in the relevant study population with non-missing data at each visit.

The minimum and maximum will be reported with the same degree of precision (i.e., the same number of decimal places) as the observed data. Measures of location (mean and median) will be reported to 1 degree of precision more than the observed data and measures of spread (SD, SE) will be reported to 2 degrees of precision more than the observed data. Plasma concentration data will be treated as three significant figures for reporting purposes. Percentages will be presented to 1 decimal place, unless otherwise specified.

Unless otherwise indicated, all statistical tests will be conducted at the 0.05 significance level using 2-tailed tests, and p-values will be reported in pvalue6.4 format. Corresponding 95% CIs will be presented for statistical tests.

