8.5. Dermal Safety

The frequency and percentage of subjects and number of patches with findings related to dermal safety including adhesion, irritation, discomfort, and adhesive residue will be summarized as described below.

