8.5.2. Irritation

Irritation will be evaluated using the following scales:

Dermal Response

- 0 = no evidence of irritation
- 1 = minimal erythema, barely perceptible
- 2 = definite erythema, readily visible; minimal edema or minimal papular response
- 3 = erythema and papules
- 4 = definite edema
- 5 = erythema, edema, and papules
- 6 = vesicular eruption
- 7 = strong reaction spreading beyond the application site

Other Effects

- A (0) = slightly glazed appearance
- B (1) = marked glazed appearance
- C (2) = glazing with peeling and cracking
- F (3) = glazing with fissures
- G (3) = film of dried serous exudates covering all or part of the patch site
- H (3) = small petechial erosions and/or scabs
- N (0) = no other observations

The frequency and percentage of subjects with patches in each combined and concatenated category will be summarized from the above scales by treatment group and overall at each visit. The Concatenated Irritation score consists of numerical “Dermal Response” score + the “Other

Effects" lettered score; for example: 2N, 2A, 3G, etc. The Combined irritation score will be calculated as a numerical total; i.e., numerical "Dermal Response" score + numeric equivalent for the "Other Effects" lettered score (note that the "Other Notations" do not have numeric equivalents and do not contribute to the numeric Combined irritation score); for example 2N, 2A, and 3G will be reported as 2, 2, and 6 combined irritations scores respectively.

In addition to the above, the frequency and percentage of subjects with a combined score of 3 or more will be tabulated.

The information from Diary data will be included in the summary table and listings.

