8.5.5. Dermal Evaluations at Home

During the Double-blind Treatment Phase at home, subjects will complete a questionnaire about adhesion, skin irritation, discomfort, and adhesive residue in the eDiary. A by-subject listing of this data will be presented in addition to summary tables for each dermal assessment.

Statistical Analysis Plan,
Sponsor Noven Pharmaceuticals, Inc.
Protocol Number HP-5000-US-05
[REDACTED]

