	xx	xx	xx (xx.x%)	xx (xx.x%)	xx (xx.x%)	xx (xx.x%)	xx (xx.x%)
	xx	xx	xx (xx.x%)	xx (xx.x%)	xx (xx.x%)	xx (xx.x%)	xx (xx.x%)
	xx	xx	xx (xx.x%)	xx (xx.x%)	xx (xx.x%)	xx (xx.x%)	xx (xx.x%)
	xx	xx	xx (xx.x%)	xx (xx.x%)	xx (xx.x%)	xx (xx.x%)	xx (xx.x%)
	xx	xx	xx (xx.x%)	xx (xx.x%)	xx (xx.x%)	xx (xx.x%)	xx (xx.x%)

Note: Percentages are $(n/N) * 100$, where N is the number of non-missing patches at a given study visit. Treatment groups are based on treatment received. Treatment arms: HP-5000-[REDACTED] topical patch, HP-5000-[REDACTED] topical patch, and Placebo. Full Descriptions:

- 0: None
- 1: Light
- 2: Medium
- 3: Heavy
- 4: Patch not present

SOURCE: Listings xx.x.x, xx.x.x

T:\Noven\HP-5000-US-05\...\xxxxxx.sas run on DDMMYYYY at HH:MM for data extracted on DDMMYYYY, on SAS v9.4

{Programming Note: continue for all applicable treatments and repeat for SUBJECT counts instead of PATCH counts}

Statistical Analysis Plan,
Sponsor Noven Pharmaceuticals, Inc.
Protocol Number HP-5000-US-05
[REDACTED]

Noven Pharmaceuticals, Inc.
Protocol HP-5000-US-05

Page 1 of x
FINAL

Table 14.3.4.1.5
Dermal Evaluations at Home – Adhesion
Safety Analysis Set

Treatment	Study Day	N (Applied Patches)	Adhesion			
			Is the patch 100% attached to the skin?		Is more than half of the patch still attached?	
			Yes n (%)	No n (%)	Yes n (%)	No n (%)
HP-5000 [REDACTED]	xx	xx	xx (xx.x%)	xx (xx.x%)	xx (xx.x%)	xx (xx.x%)
	xx	xx	xx (xx.x%)	xx (xx.x%)	xx (xx.x%)	xx (xx.x%)
	xx	xx	xx (xx.x%)	xx (xx.x%)	xx (xx.x%)	xx (xx.x%)
	xx	xx	xx (xx.x%)	xx (xx.x%)	xx (xx.x%)	xx (xx.x%)
	xx	xx	xx (xx.x%)	xx (xx.x%)	xx (xx.x%)	xx (xx.x%)
	xx	xx	xx (xx.x%)	xx (xx.x%)	xx (xx.x%)	xx (xx.x%)
Number of subjects with full detachment			xx (xx.x%)	xx (xx.x%)	xx (xx.x%)	xx (xx.x%)

Note: Percentages are $(n/N) * 100$, where N is the number of non-missing patches at a given study day with that response. Treatment groups are based on treatment received. Treatment arms: HP-5000- [REDACTED] topical patch, HP-5000- [REDACTED] topical patch, and Placebo.

SOURCE: Listings xx.x.x, xx.x.x

T:\Noven\HP-5000-US-05\...\xxxxxx.sas run on DDMMYYYY at HH:MM for data extracted on DDMMYYYY, on SAS v9.4

Table 14.3.4.1.6
 Dermal Evaluations at Home – Skin Irritation
 Safety Analysis Set

Treatment	Study Day	N (Applied Patches)	Skin Irritation					
			Any Irritation where the patch was applied?		Describe your irritation			
			Yes n (%)	No n (%)	Redness n (%)	Swelling n (%)	Itching n (%)	Other n (%)

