HP-5000-[REDACTED]	xx	xx	xx (xx.x%)	xx (xx.x%)	xx (xx.x%)	xx (xx.x%)	xx (xx.x%)	xx (xx.x%)
	xx	xx	xx (xx.x%)	xx (xx.x%)	xx (xx.x%)	xx (xx.x%)	xx (xx.x%)	xx (xx.x%)
	xx	xx	xx (xx.x%)	xx (xx.x%)	xx (xx.x%)	xx (xx.x%)	xx (xx.x%)	xx (xx.x%)
	xx	xx	xx (xx.x%)	xx (xx.x%)	xx (xx.x%)	xx (xx.x%)	xx (xx.x%)	xx (xx.x%)
	xx	xx	xx (xx.x%)	xx (xx.x%)	xx (xx.x%)	xx (xx.x%)	xx (xx.x%)	xx (xx.x%)
	xx	xx	xx (xx.x%)	xx (xx.x%)	xx (xx.x%)	xx (xx.x%)	xx (xx.x%)	xx (xx.x%)

Note: Percentages are $(n/N) * 100$, where N is the number of non-missing patches at a given study day with that response. Treatment groups are based on treatment received.

Treatment arms: HP-5000-[REDACTED] topical patch, HP-5000-[REDACTED] topical patch, and Placebo.

SOURCE: Listings xx.x.x, xx.x.x

T:\Noven\HP-5000-US-05\...\xxxxxx.sas run on DDMMYYYY at HH:MM for data extracted on DDMMYYYY, on SAS v9.4

Statistical Analysis Plan,
 Sponsor Noven Pharmaceuticals, Inc.
 Protocol Number HP-5000-US-05
 [REDACTED]

Noven Pharmaceuticals, Inc.
 Protocol HP-5000-US-05

Page 1 of x
 FINAL

Table 14.3.4.1.7
 Dermal Evaluations at Home - Discomfort
 Safety Analysis Set

Treatment	Study Day	N (Applied Patches)	Discomfort				
			Any Discomfort?		Burning	Describe Discomfort	
			Yes n (%)	No n (%)	n (%)	Itching n (%)	Pain n (%)
HP-5000-[REDACTED]	xx	xx	xx (xx.x%)	xx (xx.x%)	xx (xx.x%)	xx (xx.x%)	xx (xx.x%)
	xx	xx	xx (xx.x%)	xx (xx.x%)	xx (xx.x%)	xx (xx.x%)	xx (xx.x%)
	xx	xx	xx (xx.x%)	xx (xx.x%)	xx (xx.x%)	xx (xx.x%)	xx (xx.x%)
	xx	xx	xx (xx.x%)	xx (xx.x%)	xx (xx.x%)	xx (xx.x%)	xx (xx.x%)
	xx	xx	xx (xx.x%)	xx (xx.x%)	xx (xx.x%)	xx (xx.x%)	xx (xx.x%)
	xx	xx	xx (xx.x%)	xx (xx.x%)	xx (xx.x%)	xx (xx.x%)	xx (xx.x%)

Note: Percentages are (n/N)*100, where N is the number of non-missing patches at a given study day with that response. Treatment groups are based on treatment received.

Treatment arms: HP-5000-[REDACTED] topical patch, HP-5000-[REDACTED] topical patch, and Placebo.

SOURCE: Listings xx.x.x, xx.x.x

T:\Noven\HP-5000-US-05\...\xxxxxx.sas run on DDMMYYYY at HH:MM for data extracted on DDMMYYYY, on SAS v9.4

Statistical Analysis Plan,
 Sponsor Noven Pharmaceuticals, Inc.
 Protocol Number HP-5000-US-05
 [REDACTED]

Noven Pharmaceuticals, Inc.
 Protocol HP-5000-US-05

Page 1 of x
 FINAL

Table 14.3.4.1.8
 Dermal Evaluations at Home – Adhesive Residue
 Safety Analysis Set

Treatment	Study Day	N (Applied Patches)	Adhesive Residue	
			Yes n (%)	No n (%)
HP-5000-[REDACTED]	xx	xx	xx (xx.x%)	xx (xx.x%)

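### Home-diary tables for irritation, discomfort and residue give no count of subjects ever affected, and the footnote of all four home tables misdefines the denominator (minor)

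*SAP*

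**What the plan says.** The protocol's plan for dermal safety is by subject: "The number and percentage of subjects with findings related to dermal safety including adhesion, irritation, discomfort, and adhesive residue will be summarized" (Protocol 13.4.4.7). SAP 8.5 plans both units: "The frequency and percentage of subjects and number of patches with findings related to dermal safety including adhesion, irritation, discomfort, and adhesive residue", to be summarised as its subsections describe.

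SAP 8.5.5 covers the home evaluations and names no unit: "A by-subject listing of this data will be presented in addition to summary tables for each dermal assessment". SAP 8.5.2 and 8.5.3 plan clinic irritation and discomfort by subject. Both add that diary information goes into the summary table and the listings. SAP 8.5.4 describes residue in patches only.

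The home shells in SAP 14.2 differ from one another:

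- Table 14.3.4.1.5 (adhesion) has study-day rows in patches, then a row labelled "Number of subjects with full detachment".
- Tables 14.3.4.1.6, 14.3.4.1.7 and 14.3.4.1.8 have study-day rows in patches only. They have no subject row and no programming note.
- All four carry a column headed as N of applied patches, and a footnote computing percentages as n over N, "where N is the number of non-missing patches at a given study day with that response".

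The clinic shells for irritation, discomfort and residue carry a note to repeat the table in subject counts. Their footnotes stop at non-missing patches at the visit. The general rule in SAP 4.1 is: "The denominator for by-visit displays will be the number of subjects (or patches) in the relevant study population with non-missing data at each visit".

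**The concern.** Skin irritation, discomfort and adhesive residue are a named secondary objective. SAP section 2 describes the trial as one "with the goal to evaluate efficacy, safety (including dermal), and PK of two active treatments" ahead of phase III. For a patch, a basic tolerability question is how many subjects in each arm reacted at least once. On most treatment days the diary is the only scheduled dermal assessment, yet its tables show patches by day. They cannot separate a few subjects who react repeatedly from many who react once.

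The footnote raises a second question: what the printed percentages mean. A denominator restricted to patches with the response in question equals its own numerator. A programmer would have to depart from the stated rule, and for the descriptor columns more than one departure is plausible.

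**Working it through.** The plan states no figure to reproduce here. The check compares the shells and then does simple arithmetic.

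**1. How much of treatment rests on the diary.** The Schedule of Events (Protocol 17.1) puts on-treatment clinic dermal ratings on nominal Days 7, 14 and 28. That is 3/28 = 10.7% of days. Home-only days are 1–6, 8–13 and 15–27: 6 + 6 + 13 = 25, and 25/28 = 89.3%.

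**2. Whether daily rows determine the number of subjects ever affected.** Assumptions: one patch per subject per day, 28 days, complete diaries, and a constant daily share p of patches with a report. The application interval is redacted. About one a day is inferred from Protocol 9.9, which treats six or fewer patches a week as unsatisfactory. The values of p are assumed.

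- Fewest subjects (always the same ones): p.
- Most subjects (no repeats until everyone is affected): min(1, 28p).
- Days independent: 1 − (1 − p)^28.

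| Daily share p | Fewest | Days independent | Most |
|---|---|---|---|
| 1% | 1% | 24.5% | 28% |
| 3% | 3% | 57.4% | 84% |
| 4 of 75 = 5.3% | 5.3% (4 subjects) | 78.4% (about 59) | 100% (75) |

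The last row uses the planned active-arm size of 75. Every daily line would read 5.3% (4 × 28 = 112 of 75 × 28 = 2,100 patches over treatment), and the ever-affected count could be anything from 4 to 75. The daily rows do not determine it.

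**3. Whether another planned table supplies it.** The clinic shells use the 0–7 and 0–4 rating scales and have no diary columns. The diary's Yes/No and descriptor items do not map onto those scales. The one overall subject count among the irritation and discomfort shells is for the clinic combined score: "the frequency and percentage of subjects with a combined score of 3 or more will be tabulated". The clinic note to repeat in subject counts is itself by study day. No planned table therefore gives diary-based cumulative incidence.

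**4. The denominator.** Under the literal footnote N = n, so 1, 4, 10 or 74 positive answers all give 100%, and 0/0 is undefined. With N = 75 the same counts give 1.3%, 5.3%, 13.3% and 98.7%.

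For the descriptor columns, take an assumed day with 75 patches applied, 60 answered, 5 irritated and 4 of those red:

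- literal footnote: 4/4 = 100%
- irritated patches: 4/5 = 80%
- answered patches: 4/60 = 6.7%
- applied patches (the column header): 4/75 = 5.3%

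**The case against.** **No document promises an ever-affected count.** Protocol 13.4.4.7 does not say over what period subjects with findings are counted, and SAP 8.5 defers to its subsections. By-day or by-visit display is the plan's usual format; clinic discomfort has no ever-affected row either. At about one patch a day, a daily patch row is close to a daily subject count. This stands. A reader might infer that the SAP breaches the protocol, but the texts do not go that far. For residue the basis is thinnest, since SAP 8.5.4 speaks only of patches.

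**SAP 8.5.2 and 8.5.3 already send diary data to summaries planned by subject.** They do, and this shows an intention to report diary data alongside subject counts. They define no cumulative count, and no shell delivers one.

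**Adverse events capture it.** Protocol 10.1.2 tells subjects to report irritation, discomfort and residue to the site as well as in the diary. Protocol 11.1.1 defines adverse events broadly, sites review diaries at each treatment visit, and Table 14.3.1.2 counts each subject once per preferred term. SAP 5.1.5 also brings unscheduled dermal assessments into the summary tables. This is a substantial mitigation. However, no rule turns every positive diary answer into an adverse event, and the documents do not show how many would be missed. The listings (16.2.9.5.2 to 16.2.9.5.4) keep the diary rows by subject, but a reader would have to count by hand.

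**The footnote is a slip.** Very likely: the natural intent is patches with a non-missing answer to that question, and the shells print one N per day. It would be wrong to infer that the tables will really print 100% throughout. With n and N both printed, percentages can be rebuilt. What survives is a stated rule that is wrong as written and a real ambiguity for the descriptor columns.

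**Conclusion.** The point holds as a minor one, confined to descriptive safety tables. No planned table gives the number of subjects with at least one home report of irritation, discomfort or residue. The daily patch rows cannot stand in for it: at an assumed 3% daily share, the range is 3% to 84% of subjects. The footnote in all four home tables contradicts both the column header and SAP 4.1.

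The size rests on assumed reaction rates, complete diaries and an inferred daily patch. It shows what the tables cannot tell, not what the trial would find. A reader might infer that subject-level skin data are lost. They are not: adverse event tables hold part and listings hold the rest. No endpoint, hypothesis test or efficacy conclusion is affected.

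**What to change.** **Subject rows.** In Tables 14.3.4.1.6, 14.3.4.1.7 and 14.3.4.1.8 add, per arm, the number and percentage of subjects with at least one home report over the treatment phase. Give it overall and by descriptor where descriptors are collected (irritation and discomfort). Use as N the SAF subjects with at least one post-dose diary entry for that item.

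**Denominator.** In Tables 14.3.4.1.5 to 14.3.4.1.8:

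- delete the footnote's closing qualifier, which limits N to patches giving the response;
- define daily N as patches with a non-missing answer to the table's lead Yes/No question (for adhesion, whether the patch is fully attached);
- use the same N for follow-up and descriptor columns;
- make the column header match;
- state a subject denominator for the subject row of the home adhesion table.

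The cost is one footnote phrase and one header in four shells, plus a few descriptive rows from eDiary data already collected. No new data are needed.

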14.3. Planned Listing Shells

Noven Pharmaceuticals, Inc.
 Protocol HP-5000-US-05

Page 1 of x
 FINAL

Listing 16.2.1.1
Assignment to Analysis Populations and Treatment Cohort
All Subjects Enrolled

Subject ID	Randomization Date	Randomization ID	Randomized Treatment	ITT	FAS	SAF	PAS
XXXXX	DDMMYYYY	XXXX	Placebo	Yes	Yes	Yes	Yes
XXXXX	DDMMYYYY	XXXX	HP-5000-[REDACTED]	Yes	No; xxx xxxxxx xxxxxx xxxxx xxxxxxxx	No; xxx xxxxxx xxxxxx xxxxx xxxxxxxx	No; xxx xxxxxx xxxxxx xxxxx xxxxxxxx
XXXXX	DDMMYYYY	XXXX	Placebo	Yes	No; xxx xxxxxxxx xxxxx xxxxxxxx	No; xxx xxxxxx xxxxxx	No; xxx xxxxxxxxx
XXXXX	DDMMYYYY	XXXX	HP-5000-[REDACTED]	Yes	Yes	Yes	Yes

Note: ITT = Intent-to-Treat, FAS = Full Analysis Set, PAS = Pharmacokinetic Analysis Set, SAF = Safety Analysis Set. Treatment arms: HP-5000-[REDACTED] topical patch, HP-5000-[REDACTED] topical patch, and Placebo.

T:\Noven\HP-5000-US-05\...\xxxxxx.sas run on DDMMYYYY at HH:MM for data extracted on DDMMYYYY, on SAS v9.4

{Programming Note: If any population is listed as 'No', list the reason for exclusion from the population after a semicolon}

Statistical Analysis Plan,
 Sponsor Noven Pharmaceuticals, Inc.
 Protocol Number HP-5000-US-05
 [REDACTED]

Noven Pharmaceuticals, Inc.
 Protocol HP-5000-US-05

Page 1 of x
 FINAL

Listing 16.2.1.2
 Study Completion Status and Reasons for Discontinuation
 All Subjects Enrolled

Actual Treatment: XXXXXX

Subject ID	Screen Date	Completed Treatment?	Date Completed	Date of Discontinuation	Date of Last Contact	Date of Last Patch	Reason for Discontinuation	Date of Death Adverse Event
XXXXX	DDMMYYYY	Yes	DDMMYYYY		DDMMYYYY	DDMMYYYY		
XXXXX	DDMMYYYY	Yes	DDMMYYYY		DDMMYYYY	DDMMYYYY		
XXXXX	DDMMYYYY	No		DDMMYYYY	DDMMYYYY	DDMMYYYY	XXXXXXXXXXXXXXXXXXXX	
XXXXX	DDMMYYYY	Yes	DDMMYYYY		DDMMYYYY	DDMMYYYY		

Note: Treatment arms: HP-5000-[REDACTED] topical patch, HP-5000-[REDACTED] topical patch, and Placebo. T:\Noven\HP-5000-US-05\...\\xxxxx.sas run on DDMMYYYY at HH:MM for data extracted on DDMMYYYY, on SAS v9.4

{Programming Note: If reason discontinuation is pregnancy, or withdrawal by subject, include date after reason separated by a semicolon.

If the reason of discontinuation is adverse event, please provide this adverse event}

Statistical Analysis Plan,
 Sponsor Noven Pharmaceuticals, Inc.
 Protocol Number HP-5000-US-05
 [REDACTED]

Noven Pharmaceuticals, Inc.
 Protocol HP-5000-US-05

Page 1 of x
 FINAL

Listing 16.2.4.1
Demographics
Safety Analysis Set

Actual Treatment: XXXXXX

Subject ID	Informed Consent Date	Date of Birth	Age (yrs)	Gender	Childbearing potential?	Ethnicity	Race	Baseline Weight (kg)	Baseline Height (cm)	Baseline BMI (kg/m2)
XXXXX	DDMMYYYY	DDMMYYYY	xx	Female	Yes	xxxxxxxx	xxxxxxxxxx	xx.x	xx	xx.xx
XXXXX	DDMMYYYY	DDMMYYYY	xx	Male		xxxxxxxx	xxxxx	xx.x	xx	xx.xx
XXXXX	DDMMYYYY	DDMMYYYY	xx	Male		xxxxxx	xxxx	xx.x	xx	xx.xx
XXXXX	DDMMYYYY	DDMMYYYY	xx	Female	Yes	xxxxxxxx	xxxxxxxxxx	xx.x	xx	xx.xx

Note: Treatment arms: HP-5000-[REDACTED] topical patch, HP-5000-[REDACTED] topical patch, and Placebo. T:\Noven\HP-5000-US-05\...\\xxxxxx.sas run on DDMMYYYY at HH:MM for data extracted on DDMMYYYY, on SAS v9.4

Statistical Analysis Plan,
 Sponsor Noven Pharmaceuticals, Inc.
 Protocol Number HP-5000-US-05
 [REDACTED]

Noven Pharmaceuticals, Inc.
 Protocol HP-5000-US-05

Page 1 of x
 FINAL

Listing 16.2.4.2
 Medical History
 Safety Analysis Set

Actual Treatment: XXXXXX

Subject ID	Any History?	Ongoing at Study Start?	System Organ Class/ Preferred Term/ Verbatim Term	Start Date	End Date
XXXXX	Yes	No	XXXXXXXXXXXXXXXXXXXX/ XXXXXX/ XXXXXXXXXXXXXXXXXXXXXX	DDMMYYYY	DDMMYYYY
		Yes	XXXXXXXXXXXXXXXXXXXX/ XXXXXX/ XXXXXXXXXXXXXXXXXXXXXX	DDMMYYYY	ONGOING
XXXXX	No				
XXXXX	Yes	No	XXXXXXXXXXXXXXXXXXXX/ XXXXXX/ XXXXXXXXXXXXXXXXXXXXXX	DDMMYYYY	DDMMYYYY

Note: Medical history coded using MedDRA version 19.0. Treatment arms: HP-5000- [REDACTED] topical patch, HP-5000- [REDACTED] topical patch, and Placebo.
 T:\Noven\HP-5000-US-05\...\xxxxx.sas run on DDMMYYYY at HH:MM for data extracted on DDMMYYYY, on SAS v9.4

Statistical Analysis Plan,
 Sponsor Noven Pharmaceuticals, Inc.
 Protocol Number HP-5000-US-05
 [REDACTED]

Noven Pharmaceuticals, Inc.
 Protocol HP-5000-US-05

Page 1 of x
 FINAL

Listing 16.2.4.3
 Concomitant and Prior Medications
 Safety Analysis Set

Actual Treatment: XXXXXXX

Subject ID	Prior	Concomitant	Anatomic Therapeutic Class/ Preferred Term/ Verbatim Term	Start Date/ End Date	Indication: Pre-Existing	Onset	Dose (unit)/ Dose Form/ Route/ Frequency
						Indication: AE from Therapeutic Use	
XXXXX	Yes	No	XXXXXXXXXXXXXXXXXXXX/	DDMMYYYY/ DDMMYYYY	xxxxxxxxx	xxxxxx	XXXXXXXXXXXXXXXXXXXX <units> /
			XXXXXXX/				XXXXXXXXXXXX
			XXXXXXXXXXXXXXXXXXXXXX				XXXXXX/
			XXXXXXXXXXXXXXXXXXXX/	DDMMYYYY/ ONGOING	xxxxxxxx	xxxxxx	XXXXXXXXXXXXXXXXXXXX <units> /
			XXXXXXX/				XXXXXXXXXXXX
			XXXXXXXXXXXXXXXXXXXXXX				XXXXXX/
							XXXXXXXXXXXXXXXXXXXXXX
XXXXX	No	Yes					

Note: Medication coded using WHO-DD (Enhanced version 2017), ATC level 4. Treatment arms: HP-5000-[REDACTED] topical patch, HP-5000-[REDACTED] topical patch, and Placebo. T:\Noven\HP-5000-US-05\...\xxxxxx.sas run on DDMMYYYY at HH:MM for data extracted on DDMMYYYY, on SAS v9.4

{Programming Note: If indication is pre-existing or adverse event, please add MH/AE number to indication separated by a semi-colon. Please add all abbreviations that are not units that present on this table}

Statistical Analysis Plan,
 Sponsor Noven Pharmaceuticals, Inc.
 Protocol Number HP-5000-US-05
 [REDACTED]

Noven Pharmaceuticals, Inc.
 Protocol HP-5000-US-05

Page 1 of x
 FINAL

Listing 16.2.5.1
Drug Accountability and Compliance
Safety Analysis Set

Actual Treatment: XXXXXX

Subject ID	Visit	Dispense Date (Study Day)	Treatment					Overall Compliance (%) [1]
			Duration (days)	Kit Number	Dispensed Amount	Date Returned	Returned Amount	
XXXXX	Week 1	DDMMYY (xx)	xx	XXXXXX	XX	DDMMYY	XX	xx.x%
	Week 2	DDMMYY (xx)	xx	XXXXXX	XX	DDMMYY	XX	
	Week 4	DDMMYY (xx)	xx	XXXXXX	XX	DDMMYY	XX	
XXXXX	Week 1	DDMMYY (xx)	xx	XXXXXX	XX	DDMMYY	XX	xx.x%
	Week 2	DDMMYY (xx)	xx	XXXXXX	XX	DDMMYY	XX	
	Week 4	DDMMYY (xx)	xx	XXXXXX	XX	DDMMYY	XX	

Note: Treatment arms: HP-5000-[REDACTED] topical patch, HP-5000-[REDACTED] topical patch, and Placebo. [1] Compliance is defined as the number of patches given less the number of patches returned divided by the number of days for required applications (e.g. without counting of extra patches given just in case), expressed as a percentage.

T:\Noven\HP-5000-US-05\...\xxxxxx.sas run on DDMMYY at HH:MM for data extracted on DDMMYY, on SAS v9.4

Statistical Analysis Plan,
 Sponsor Noven Pharmaceuticals, Inc.
 Protocol Number HP-5000-US-05
 [REDACTED]

Noven Pharmaceuticals, Inc.
 Protocol HP-5000-US-05

Page 1 of x
 FINAL

Listing 16.2.5.2
 Plasma Concentration
 Pharmacokinetic Analysis Set

Actual Treatment: XXXXXXX

Subject ID	Visit	Dosing Date and Time	Was PK Sample collected?	Reason Not Collected	Sample Collection Date	Time Blood Drawn	Plasma Concentration (ng/mL)
XXXXX	Week 2	DDMMYY/HH:MM	Yes		DDMMYY/HH:MM	HH:MM	xx.xx
	Week 4	DDMMYY/HH:MM	Yes		DDMMYY/HH:MM	HH:MM	xx.xx
XXXXX	Week 2	DDMMYY/HH:MM	No	xxxxxxxxxx	DDMMYY/HH:MM	HH:MM	xx.xx
	Week 4	DDMMYY/HH:MM	Yes		DDMMYY/HH:MM	HH:MM	xx.xx
XXXXX	Week 2	DDMMYY/HH:MM	Yes		DDMMYY/HH:MM	HH:MM	xx.xx
	Week 4	DDMMYY/HH:MM	Yes		DDMMYY/HH:MM	HH:MM	xx.xx
XXXXX	Week 2	DDMMYY/HH:MM	No	xxxxxxxxxxxxxxxxxx			
	Week 4	DDMMYY/HH:MM	No	xxxxxxxxxxxxxx			

Note: Treatment arms: HP-5000-[REDACTED] topical patch, HP-5000-[REDACTED] topical patch, and Placebo.

T:\Noven\HP-5000-US-05\...\xxxxxx.sas run on DDMMYY at HH:MM for data extracted on DDMMYY, on SAS v9.4

Statistical Analysis Plan,
 Sponsor Noven Pharmaceuticals, Inc.
 Protocol Number HP-5000-US-05
 [REDACTED]

Noven Pharmaceuticals, Inc.
 Protocol HP-5000-US-05

Page 1 of x
 FINAL

Listing 16.2.6.1.1
 WOMAC Items
 Full Analysis Set

Actual Treatment: XXXXXX

Subject ID	Date	Visit/ Assessment		Pain [1]		Stiffness [2]		Physical Function [3]																
		1	2	3	4	5	1	2	1	2	3	4	5	6	7	8	9	10	11	12	13	14	15	16
XXXXX	Baseline/ DDMMYYYY	x	x	x	x	x	x	x	x	x	x	x	x	x	x	x	x	x	x	x	x	x	x	x
	Week 1/ DDMMYYYY	x	x	x	x	x	x	x	x	x	x	x	x	x	x	x	x	x	x	x	x	x	x	x
	Week 2/ DDMMYYYY	x	x	x	x	x	x	x	x	x	x	x	x	x	x	x	x	x	x	x	x	x	x	x
	Week 4/ DDMMYYYY	x	x	x	x	x	x	x	x	x	x	x	x	x	x	x	x	x	x	x	x	x	x	x

Note: Individual WOMAC scores are evaluated based on a likert scale and range from 0 = None, 1 = Mild, 2 = Moderate, 3 = Severe, 4 = Extremely. WOMAC = West Ontario and McMasters Universities Osteoarthritis Index. Treatment arms: HP-5000-[REDACTED] topical patch, HP-5000-[REDACTED] topical patch, and Placebo..

[1] 1. Walking, 2. Stair Climbing, 3. Nocturnal, 4. Rest, 5. Weight bearing.

[2] 1. Morning stiffness, 2. Stiffness occurring later in the day.

[3] 1. Descending stairs, 2. Ascending Stairs, 3. Rising from sitting, 4. Standing, 5. Bending to floor, 6. Walking on flat surface, 7. Getting in/out of car, 8. Going shopping, 9. Putting on socks, 10. Lying in bed, 11. Taking off socks, 12. Rising from bed, 13. Getting in/out of bath, 14. Sitting, 15. Getting on/off toilet, 16. Heavy domestic duties, 17. Light domestic duties.

T:\Noven\HP-5000-US-05\...\xxxxxx.sas run on DDMMYYYY at HH:MM for data extracted on DDMMYYYY, on SAS v9.4

Statistical Analysis Plan,
 Sponsor Noven Pharmaceuticals, Inc.
 Protocol Number HP-5000-US-05
 [REDACTED]

Noven Pharmaceuticals, Inc.
 Protocol HP-5000-US-05

Page 1 of x
 FINAL

Listing 16.2.6.1.2
 WOMAC Scores
 Full Analysis Set

Actual Treatment: XXXXXX

Subject ID	Visit	Assessment Date	Pain Score [1]	Stiffness Score [2]	Physical Function Score [3]	Composite Score [4]
XXXXX	Baseline	DDMMYY	xx	xx	xx	xx
	Week 1	DDMMYY	xx	xx	xx	xx
	Week 2	DDMMYY	xx	xx	xx	xx
	Week 4	DDMMYY	xx	xx	xx	xx
XXXXX	Baseline	DDMMYY	xx	xx	xx	xx
	Week 1	DDMMYY	xx	xx	xx	xx
	Week 2	DDMMYY	xx	xx	xx	xx
	Week 4	DDMMYY	xx	xx	xx	xx

Note: WOMAC = West Ontario and McMasters Universities Osteoarthritis Index. Treatment arms: HP-5000- [REDACTED] topical patch, HP-5000- [REDACTED] topical patch, and Placebo.

[1] Range from 0 to 20 by summing each item relating to Pain.

[2] Range from 0 to 8 by summing each item relating to Stiffness.

[3] Range from 0 to 68 by summing each item relating to Physical Function.

[4] Calculated by summing the items for all 3 subscales (Pain, Stiffness, and Physical Function) and then dividing by 96. Higher scores on the WOMAC indicate worse pain, stiffness, and functional limitations.

T:\Noven\HP-5000-US-05\...\xxxxxx.sas run on DDMMYY at HH:MM for data extracted on DDMMYY, on SAS v9.4

Statistical Analysis Plan,
 Sponsor Noven Pharmaceuticals, Inc.
 Protocol Number HP-5000-US-05
 [REDACTED]

Noven Pharmaceuticals, Inc.
 Protocol HP-5000-US-05

Page 1 of x
 FINAL

Listing 16.2.6.2
 Patient Global Assessment (PGA)
 Full Analysis Set

Actual Treatment: XXXXXXX

Subject ID	Visit	Assessment Date	How would you rate your osteoarthritis condition over the last 24 hours?
XXXXX	Baseline	DDMMYY	XXXXXXXXXXXXXXXXXXXXXXXXXX
	Week 1	DDMMYY	XXXXXX
	Week 2	DDMMYY	XXXXXXXXXXXXXXXXXXXX
	Week 4	DDMMYY	XXXXXXXXXXXX
XXXXX	Baseline	DDMMYY	XXXXXXXXXXXXXX
	Week 1	DDMMYY	XXXXXX
	Week 2	DDMMYY	XXXXXXXXXXXXXXXXXXXXXX
	Week 4	DDMMYY	XXXXXXXXXXXXXXXXXXXXXX

Note: PGA is a 1 to 7 scale where 1 = "Very Much Improved", 2 = "Much Improved", 3 = "Minimally Improved", 4 = "No Change", 5 = "Minimally Worse", 6 = "Much Worse", and 7 = "Very Much Worse". Treatment arms: HP-5000- [REDACTED] topical patch, HP-5000- [REDACTED] topical patch, and Placebo.

T:\Noven\HP-5000-US-05\...\xxxxxx.sas run on DDMMYY at HH:MM for data extracted on DDMMYY, on SAS v9.4

Statistical Analysis Plan,
 Sponsor Noven Pharmaceuticals, Inc.
 Protocol Number HP-5000-US-05
 [REDACTED]

Noven Pharmaceuticals, Inc.
 Protocol HP-5000-US-05

Page 1 of x
 FINAL

Listing 16.2.6.3
 Patient Global Impression (PGI) of Change
 Full Analysis Set

Actual Treatment: XXXXXXX

Subject ID	Visit	Assessment Date	How would you rate your overall improvement with treatment during the clinical trial?
XXXXX	Week 1	DDMMYY	XXXXXXXX
	Week 2	DDMMYY	XXXXXXXXXXXXXXXXXXXX
	Week 4	DDMMYY	XXXXXXXXXXXX
XXXXX	Week 1	DDMMYY	XXXXXXXXXXXX
	Week 2	DDMMYY	XXXXXXXXXXXXXXXXXXXX
	Week 4	DDMMYY	XXXXXXXXXXXXXXXX

Note: PGI is a 0 to 4 scale where 0 = "Very Good", 1 = "Good", 2 = "Moderate", 3 = "Poor", and 4 = "Very Poor". Treatment arms: HP-5000-[REDACTED] topical patch,
 HP-5000-[REDACTED] topical patch, and Placebo.

T:\Noven\HP-5000-US-05\...\xxxxxx.sas run on DDMMYY at HH:MM for data extracted on DDMMYY, on SAS v9.4

Statistical Analysis Plan,
 Sponsor Noven Pharmaceuticals, Inc.
 Protocol Number HP-5000-US-05
 [REDACTED]

Noven Pharmaceuticals, Inc.
 Protocol HP-5000-US-05

Page 1 of x
 FINAL

Listing 16.2.6.4
Pain Intensity Assessed on an 11-Point Numeric Rating Scale (NRS)
Full Analysis Set

Actual Treatment: XXXXXXX

Subject ID	Visit	Assessment Date	Worst NRS Pain		Worst NRS Pain Score [2]	Overall NRS Pain (Target Knee)	Overall NRS Pain (Non-Target Knee)	Average NRS Pain Score [1]
			(Target Knee)	(Non-Target Knee)				
XXXXX	Diary	DDMMYY	xx	xx		xx	xx	
	Diary	DDMMYY	xx	xx		xx	xx	
	Diary	DDMMYY	xx	xx		xx	xx	
	Baseline	DDMMYY	xx	xx	xx	xx	xx	xx
	Diary	DDMMYY	xx	xx		xx	xx	
	Diary	DDMMYY	xx	xx		xx	xx	
	Diary	DDMMYY	xx	xx		xx	xx	
	Diary	DDMMYY	xx	xx		xx	xx	
	Diary	DDMMYY	xx	xx		xx	xx	
	Week 1	DDMMYY	xx	xx	xx	xx	xx	xx

Note: NRS is an 11-point scale from 0 to 10 where 0 = no pain and 10 = the worst pain imaginable, a value in the middle, around 5 would be moderate pain; a value of 2 or 3 would be mild pain and value of 7 or higher is considered severe pain. Treatment arms: HP-5000-[REDACTED] topical patch, HP-5000-[REDACTED] topical patch, and Placebo.

[1] Average of NRS pain scores reported for pain over the last 24 hours for the last 3 days prior to each clinic or phone visit.

[2] Worst NRS pain score reported for pain over the last 24 hours for the last 3 days prior to each clinic or phone visit

T:\Noven\HP-5000-US-05\...\xxxxxx.sas run on DDMMYY at HH:MM for data extracted on DDMMYY, on SAS v9.4

Statistical Analysis Plan,
 Sponsor Noven Pharmaceuticals, Inc.
 Protocol Number HP-5000-US-05
 [REDACTED]

Noven Pharmaceuticals, Inc.
 Protocol HP-5000-US-05

Page 1 of x
 FINAL

Listing 16.2.6.5
 Rescue Medication Use
 Full Analysis Set

Actual Treatment: XXXXXXX

Subject ID	Visit (Study Day)	Rescue medication dispensed?	Medication Name/ Bottle No./ Date Dispensed	Dispensed Amount (units)	Date Dispensed/ Date Returned	Returned Amount (units)	Lose Dose YN?	Reason
XXXXX	Baseline (xx)	No						
	Week 1 (xx)	No						
	Week 2 (xx)	Yes	xxxxxxxxxxxxxxxxxxxxxx xxxxxxxx/ xxxxx	xxxx (xxx)	DDMMYYYY/ DDMMYYYY	xxxx (xxx)	No	
	Week 4 (xx)	Yes	xxxxxxxxxxxx/ xxxx	xxxx (xxx)	DDMMYYYY/ DDMMYYYY	xxxx (xxx)	No	
XXXXX	Baseline (xx)	Yes	xxxxxxxxxxxxxxxxxxxxxx xxxxxxxx/ xxxxx	xxxx (xxx)	DDMMYYYY/ DDMMYYYY	xxxx (xxx)	No	
	Week 1 (xx)	Yes	xxxxxxxxxxxx/ xxxx	xxxx (xxx)	DDMMYYYY/ DDMMYYYY	xxxx (xxx)	Yes	xxxxxxxxxxxx
	Week 2 (xx)	No						
	Week 4 (xx)	No						

Note: Study Day = Dispense Date – Date of First Dose + 1. Treatment arms: HP-5000- [REDACTED] topical patch, HP-5000- [REDACTED] topical patch, and Placebo.
 T:\Noven\HP-5000-US-05\...\xxxxxx.sas run on DDMMYYYY at HH:MM for data extracted on DDMMYYYY, on SAS v9.4

Statistical Analysis Plan,
 Sponsor Noven Pharmaceuticals, Inc.
 Protocol Number HP-5000-US-05
 [REDACTED]

Noven Pharmaceuticals, Inc.
 Protocol HP-5000-US-05

Page 1 of x
 FINAL

Listing 16.2.7.1
Adverse Events
Safety Analysis Set

Actual Treatment: XXXXXX

Subject ID	AE Number	System Organ Class/ Preferred Term/ Verbatim Term	Start Date/ Start Time (Study Day)	End Date/ End Time	Event Duration (days)	Severity/ Relationship to Study Drug	Outcome/ Action Taken with Study Medication	Serious? /Disc.	CA/DIS/HO/ DE/LT/OTH/ OA/DISC
XXXXX	xxx	xxxxxxxxxx xxxx xxxx/ xxxxxxxxxxxxxxxxxx/ xxxxxxxxxxxxxxxxxx	DDMMYYYY/ HH:MM (xx)	DDMMYYYY/ HH:MM	xxx	xxxxxx/ xxxxxxxxxxxxxx	xxxxxxxxxxxxxx/ xxxxxxxxxxxxxx	No/No	No/No/No/ No/No/No/ No/No
	xxx	xxxxxxxxxx xxxx xxxx/ xxxxxxxxxxxxxxxxxx/ xxxxxxxxxxxxxxxxxx	DDMMYYYY/ HH:MM (xx)	ONGOING	xxx	xxxxxx/ xxxxxxxxxxxxxx	xxxxxxxxxxxxxx/ xxxxxxxxxxxxxx	Yes/Yes	No/No/Yes/ No/No/Yes No/Yes
XXXXX	xxx	xxxxxxxxxx xxxx xxxx/ xxxxxxxxxxxxxxxxxx/ xxxxxxxxxxxxxxxxxx	DDMMYYYY/ HH:MM (xx)	DDMMYYYY/ HH:MM	xxx	xxxxxx/ xxxxxxxxxxxxxx	xxxxxxxxxxxxxx/ xxxxxxxxxxxxxx	No/No	No/No/No/ No/No/No/ No/No

Note: Study Day = AE Start Date – Date of First Dose + 1. Adverse Events coded using MedDRA version 19.0. CA = congenital abnormality, DE = death, DIS = disability, Disc. = discontinued from study, DISC = Did AE cause discontinuation from the study?, HO = hospitalization, LT = life threatening, OA = other action, OTH = other medically important event. Treatment arms: HP-5000 [REDACTED] topical patch, HP-5000 [REDACTED] topical patch, and Placebo.

T:\Noven\HP-5000-US-05\...\xxxxxx.sas run on DDMMYYYY at HH:MM for data extracted on DDMMYYYY, on SAS v9.4

{Programming Note: if other action is populated, concatenate with action taken with study medication separated by semi-colon}

Statistical Analysis Plan,
Sponsor Noven Pharmaceuticals, Inc.
Protocol Number HP-5000-US-05
